	
20. Any autoimmune or immunodeficiency disease/condition (inherited or iatrogenic).
 
21. Any medical condition which, in the opinion of the investigator, might interfere with the evaluation of the study objectives or might affect the safety of the individual, e.g. evolving encephalopathy not attributable to another identifiable cause within 7 days of administration of a previous dose of any vaccine, hospitalization due to major depression or history of suicidal attempt.
 
22. Abnormal laboratory values outside the limit of normal values for the screening laboratory with clinical significance at the discretion of the investigator.
 
23. Person in frequent contact with children less than 1 year of age (parent, childcare worker, nurse, etc) or residence in the same household as persons with known immunodeficiency including persons on immunosuppressant therapy.

Temporary contra-indications to vaccination	
Reschedule vaccination and visit 2 if
 
 • Febrile illness (oral temperature $\geq 38.0^{\circ}\text{C}$) at the day of vaccination. • Upper respiratory infection (URI), rhinitis and/or rhinoconjunctivitis.
Investigational product	Live attenuated Bordetella pertussis BPZE1 strain or placebo
Presentation	Vial
Dose	2 x 0.4 mL (0.4 mL per nostril)
Route	Nasal
Vaccination schedule	Drops administered by tuberculin syringes, one syringe containing 0.4 mL for each nostril at visit 2 (0.4 mL per nostril containing half the dose 5×10^6 ; 5×10^7 ; 5×10^8 bacteria to give a total dose of 10^7 ; 10^8 ; 10^9 , respectively.).
Duration of treatment:	Single administration at day 0

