B. pertussis has not been shown to be allergenic in any preclinical or clinical studies to date. On the contrary the BPZE1 has been demonstrated to protect against airway inflammations induced by allergens or viral infections in a mouse model. The BPZE1 has also been shown to protect against infection with wild type *B. pertussis* infection already 3 hours after immunization in a mouse model (Mielcarek et al., Live attenuated *B. pertussis* as a single-dose nasal vaccine against whooping cough. PLoS Pathog 2006;2:e65).

The BPZE1 vaccine or placebo will be administered nasally via tuberculin syringes to healthy adult volunteers under strictly controlled conditions at the Karolinska Trial Alliance phase I unit. To minimize the risk of transmission the volunteers will stay at the study centre for 6 hours after administration of the vaccine. In addition volunteers with frequent contact with infants below one year of age or individuals with immunodeficiency will be excluded from participation in the study. The attenuated BPZE1 bacteria colonize the upper respiratory tract similarly to the wild-type *B. pertussis*. Colonization of live organism will be followed in nasopharyngeal aspirates performed at various intervals from the day of administration until the end of the study. Chronic carriage of *B. pertussis* has not been reported and is therefore not expected.

To avoid accidental exposure actions should be taken to minimize generation of aerosols, since the bacteria is strictly a respiratory tract organism. The volunteers and the staff members should wear eye-protective glasses during the vaccination. Persons handling the BPZE1 bacteria should wear gloves and must wash their hands with a suitable disinfecting soap before touching their skin and eyes. Effective antibiotic treatment with e.g. erythromycin will be given in case of accidental transmission to other humans.

Female mice when vaccinated with BPZE1 shortly before mating showed no negative effect on their pregnancy nor on their offspring. As a matter of fact, the offspring were protected against *B. pertussis* challenge.

In summary, the risk assessment for this study shows a very low potential risk for the volunteers and impact associated with administering the BPZE1.

IV. Study objectives

IV.1. PRIMARY OBJECTIVE: SAFETY

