- 2) the levels of cytokine after stimulation of PBMC with *B. pertussis* antigens and unrelated antigens.
- 3) the cytokine levels in nasopharyngeal aspirate.

To explore the frequency and magnitude of colonization and as well as antibody, B and T cell responses in a small group of healthy adult volunteers with high PRN antibody levels (only highest vaccine dose).

V. Selection of volunteers

V.1. INCLUSION CRITERIA

Subject will be included in the study if he/she meets all the following criteria:

1. Healthy male or female between 18 and 32 years of age, vaccinated or unvaccinated with acellular pertussis vaccine.
2. Female subject of child bearing potential must be willing to ensure to use one of the following methods of contraception from 2 weeks before vaccination till one month after vaccination to avoid pregnancy during the study:
 - Complete abstinence from penile-vaginal intercourse
 - Double barrier method (male condom/spermicide, male condom/diaphragm, diaphragm/spermicide)
 - Any intrauterine device (IUD) with published data showing that the expected failure rate is <1% per year
 - Approved hormonal contraception (except low-dose gestagen), which is not contraindicated to study vaccine administration
3. Informed consent form (ICF) signed by the subject.
4. Subject shall be able to attend all scheduled visits and to understand and comply with the study procedures.

V.2. EXCLUSION CRITERIA

If any of the following criteria are met, the subject must not be included in the study:

1. Individual with PT and /or PRN serum IgG antibodies ≥ 20 IU/ml. NOTE! One control group with PRN serum IgG antibodies ≥ 20 IU/ml and PT serum IgG antibodies <20 IU/ml will be included.
2. Vaccinated with the study vaccine in the Child Innovac study (EudraCT number 2010-019936-11).
3. Pregnant or lactating women. Pregnancy not planned and to be avoided during the study by use of effective contraceptive methods.
4. Blood pressure after resting $\geq 150/90$ mm Hg at screening.
5. Heart rate after resting ≥ 80 bpm at screening.
6. Respiratory rate after resting ≥ 20 /minute at screening.
7. Unwillingness to refrain from the use of nicotine products from screening through day 28.
8. Use of narcotic drugs and/or a history of drug/alcohol abuse within the past 2 years prior to screening.
9. The subject has donated blood or suffered from blood loss of at least 450 ml (1 unit of blood) within 60 days prior to screening or donated plasma within 14 days prior to screening.

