10. Receipt of immunoglobulin, blood derived products, systemic corticosteroids or other immunosuppressant drugs within 90 days prior to day 0.
11. Asthma or other chronic respiratory problems.
12. Use of corticosteroids in the respiratory tract (e.g. nasal steroids, inhaled steroids) 30 days prior to day 0.
13. Receipt of a vaccine within the last 30 days prior to day 0 or planned vaccination within the next 30 days after day 0.
14. Known hypersensitivity to any component of the study vaccine.

15. Current participation in any other clinical trial or participation (and during the whole study) in any clinical trial in the previous 3 months prior to day 0.
16. Inability to adhere to the protocol, including plans to move from the area.
17. Family history (first degree) of congenital or hereditary immunodeficiency.
18. Past or present infection with HIV, hepatitis B or C.
19. Chronic conditions requiring ongoing active medical interventions, such as diabetes mellitus or cardiovascular disease.
20. Any autoimmune or immunodeficiency disease/condition (inherited or iatrogenic).
21. Any medical condition which, in the opinion of the investigator, might interfere with the evaluation of the study objective or might affect the safety of the individual, e.g. evolving encephalopathy not attributable to another identifiable cause within 7 days of administration of a previous dose of any vaccine, hospitalization due to major depression or history of suicidal attempt. .
22. Abnormal laboratory values outside the limit of normal values for the screening laboratory with clinical significance at the discretion of the investigator.
23. Person in frequent contact with children less than 1 year of age (parent, childcare worker, nurse, etc) or residence in the same household as persons with known immunodeficiency including persons on immunosuppressive treatment.

V.3. TEMPORARY CONTRAINDICATIONS

Reschedule vaccination and visit 2 if

- Febrile illness and/or oral temperature $\geq 38.0^{\circ}\text{C}$ at the time of vaccination.
- Upper respiratory infection (URI), rhinitis and/or rhinoconjunctivitis.

VI. Study plan and design

VI.1. PLANNED STUDY CALENDAR

FVFS	August 2015
FVLS	February 2016
LVLS	September 2016
Antibody assays	August 2015 – October 2016
Exploratory laboratory assays	April 2016 – December 2016
Statistical analysis	October 2016 – December 2016

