- Visit 8, 28 (- 1; +7) days after visit 2: physical examination, safety follow up of vaccination and collection of blood, urine (females only) and nasopharyngeal sample.

- Visit 8, 45 (-5; +10) days after visit 2: physical examination, safety follow up of vaccination and collection of nasopharyngeal sample in volunteers in which BPZE1 bacteria were still detectable on day 28 (- 1; +7).
- Visit 9, 6±1 months after visit 2: physical examination, safety follow up of vaccination and collection of blood and nasopharyngeal sample.

VI.3.1. First contact

The clinical trial site will either find the healthy volunteers by the use of Karolinska Trial Alliance database or by advertising in the local periodicals or on Facebook.

All subjects will have a personal contact by phone and a screening visit can be booked.

Written information about the study will be sent to the potentially healthy volunteers before they come to their first visit at the clinic.

VI.3.2. Visit 1, screening 1-6 weeks before vaccination

During this visit the investigator will:

1. Inform the subject about the study and obtain a signed ICF. ICF should be dated and signed by the volunteer and the investigator before any study-related activities take place.
2. Verify the subject's eligibility by reviewing inclusion and exclusion criteria.
3. Assign a unique screening number to the subject (refer to section VI.4. "Screening number and randomization procedure").
4. Collect information regarding the subject's demography. Record the information in the CRF.
5. Collect information regarding the subject's personal and medical history and concomitant treatment as defined in section VII.1. "Prior medications and vaccination". Record the information in the CRF.
6. Perform a full physical examination including ECG and measure
 - a) oral temperature
 - b) blood pressure
 - c) pulse
 - d) respiratory rate
 - e) height
 - f) weightand record the information in the subject's eCRF
7. Collect blood samples as described in section XII.3. "Blood samples". Complete the appropriate document provided in the investigator or delegate Site file.
8. Collect urine samples as described in section XII.5. "Urine samples". Complete the appropriate document provided in the investigator or delegate Site file.

VI.3.3. Visit 2, day 0, vaccination

During this visit the investigator or delegate will:

1. Verify the subject's eligibility by reviewing inclusion and exclusion criteria.

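### For immunodeficient contacts, exclusion criterion 23 reaches only the volunteer's own household, while the risk assessment says frequent contact is excluded; the criterion also has no forward window

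*Combined protocol and SAP*

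**What the plan says.** Protocol III.3, in the volunteers' risk assessment, gives a first containment measure: "To minimize the risk of transmission the volunteers will stay at the study centre for 6 hours after administration of the vaccine". The next sentence opens as an addition to it and says that "volunteers with frequent contact with infants below one year of age or individuals with immunodeficiency will be excluded from participation in the study".

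The rule the site applies is exclusion criterion 23 in V.2. Its first part reads "Person in frequent contact with children less than 1 year of age (parent, childcare worker, nurse, etc", where the list in brackets gives examples. Its second part reads "residence in the same household as persons with known immunodeficiency including persons on immunosuppressive treatment". The synopsis carries the same second part with one word changed at the end: "residence in the same household as persons with known immunodeficiency including persons on immunosuppressant therapy". SAP 3.1.1 repeats the V.2 wording.

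Other criteria in the same list look ahead. Criterion 7 is "Unwillingness to refrain from the use of nicotine products from screening through day 28", and criterion 13 includes "planned vaccination within the next 30 days after day 0". Criterion 23 names no period.

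On carriage, IV.1 labels the 28 days after vaccination the colonization period. III.2 reports that colonization in the earlier trial was found between Day 4 and Day 28. VI.3 adds an extra visit (Visit 8') for "collection of nasopharyngeal sample in volunteers in which BPZE1 bacteria were still detectable on day 28".

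**The concern.** The benefit/risk text describes an enrolled population that the eligibility list does not produce. The people exposed by the difference are third parties who have not consented, and the risk assessment itself picks them out as needing protection.

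The wording at entry matters more than usual because of the blinding rules. Under II.3, culture results stay inside the laboratory, and the investigator hears of carriage only if the Day 28 sample is positive. Up to that visit neither site nor volunteer knows who is colonized, so contact cannot be managed according to carriage status. In the criteria and visit procedures as written, selection at entry is the only control on whom a carrier meets after leaving the centre.

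The mismatch would also go unseen in the analysis. For criterion 23, SAP 3.1.1 has the statistician check only that the recorded answer is no. A volunteer with frequent non-household contact answers no correctly and is not counted as an eligibility deviation.

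**Working it through.** The main check is a comparison of texts.

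| Element | III.3 risk assessment | Criterion 23 (V.2, synopsis, SAP 3.1.1) | Same scope? |
|---|---|---|---|
| Infants under 1 year | frequent contact | frequent contact | yes |
| Immunodeficient persons | frequent contact | shared household only | no |
| Qualifier on immunodeficiency | none | must be known; persons under immunosuppression included | no |
| Period covered | none stated | none stated | yes, both silent |

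1. *Scope.* The bracketed examples in criterion 23, including nurse, belong to the infant part. A nurse on a ward for immunosuppressed patients who lives with no such person meets neither part. The same holds for someone who regularly cares for an immunosuppressed parent at another address. Both are excluded by III.3 and eligible under V.2. All three statements of the criterion agree, so this is not a slip in one copy.

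2. *Timing.* Eligibility is verified at Visit 1 (VI.3.2, step 2) and Visit 2 (VI.3.3, step 1), both before dosing, and not again. The criterion is in the present tense. A volunteer whose partner is due two weeks after Day 0 passes both reviews, then has daily infant contact within the 28-day period. The procedures for Visits 2 to 9, including Visit 8', contain no question or instruction on contacts with infants or immunodeficient persons.

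3. *Scale of carriage.* Inputs: 12 active recipients in each of groups 1 to 3 and 6 in group 4 (VI.2); 5 of 12 colonized at 10^7 cfu in the earlier trial (III.2).
   - Active recipients: 12 × 3 + 6 = 42.
   - Earlier rate: 5/12 = 41.7%, exact 95% interval 15.2% to 72.3%.
   - Carriers at that rate: 42 × 5/12 = 17.5. Over the interval: 42 × 0.152 = 6.4 to 42 × 0.723 = 30.4.
   - The top dose is 10^9/10^7 = 100 times the earlier maximum and goes to 12 + 6 = 18 of the 42.

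   Applying the earlier rate to all 42 is an assumption. The documents give no rate at 10^8 or 10^9, and volunteers here are selected on antibody level. These figures count possible carriers. How many of them would have the contacts at issue is not given.

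4. *Length of the period.* Visit 8 is Day 28 (-1; +7), so a period running through Visit 8 ends by Day 28 + 7 = 35 and covers the 28 days named in IV.1.

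**The case against.** The III.3 sentence is background prose and can be parsed another way, as excluding individuals who are themselves immunodeficient, which criterion 20 already does. On that reading nothing conflicts. The reading is strained: the sentence follows directly from the one on transmission and is presented as a further measure to the same end, so contact is its natural subject. That the sentence can be parsed two ways is another reason to reword it.

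It is also fair that III.3 does not rest on this exclusion alone. It judges transmission very improbable because tracheal cytotoxin is reduced by more than 95% and coughing is not expected. It reports no cross-contamination between volunteers in the earlier trial and provides for antibiotic treatment after accidental transmission. This lowers the stakes but leaves the mismatch, because the authors wanted a contact exclusion even so.

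A reader might infer more than the documents support:

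- *That criterion 23 is narrower throughout.* It is not; the infant part has the same scope in both places.
- *That the missing window contradicts III.3.* III.3 has no window either, so this is a shared omission.
- *That volunteers get no advice on contacts.* The consent pages, the standard operating procedure cited at Visit 2 and the content of Appendix 2 were not available and may contain it. The finding is limited to the criteria and visit procedures.
- *That this trial aims at more than 70% colonization.* III.2 says that of future trials; it is not an objective or endpoint here.
- *That the entry criterion should run to Visit 8', which can fall as late as Day 45 + 10 = 55.* Whether Visit 8' takes place depends on the Day 28 culture, which is unknown at entry.

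**Conclusion.** The point holds in two parts of unequal strength. The first is a contradiction: for immunodeficient contacts, III.3 claims an exclusion by frequent contact that criterion 23 does not make, so frequent non-household contacts can be enrolled. This rests on the natural reading of III.3 and needs no numerical assumption. The second is a gap: with no forward window, criterion 23 admits someone whose infant contact is expected to begin during the protocol's own colonization period, although criteria 7 and 13 show that the list looks ahead where its authors meant it to.

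The number of volunteers affected cannot be derived from the documents. About 17 of 42 carriers, from the earlier rate, gives only the order of magnitude of carriage. No analysis, sample size or estimate changes. The consequence is for third-party safety and for the accuracy of the risk statement. The correction should be made; the protocol's own view that transmission is improbable keeps it from being more serious.

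**What to change.** 1. Reconcile the III.3 sentence with criterion 23 in V.2, the synopsis and SAP 3.1.1, so that one contact definition applies to immunodeficient persons. Whether that is frequent contact or shared household is for the sponsor to decide. If the household rule stays, III.3 should state that narrower exclusion.
2. Word criterion 23 as current or expected contact over a stated period from Day 0 that covers at least the colonization period, that is, through Visit 8. An infant expected in the household within that period should count.
3. Ask the question within the eligibility reviews that Visits 1 and 2 already contain. No new procedure is needed.

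The cost is a change of wording in one criterion and one background sentence, carried through the synopsis and SAP, and a few more screen failures.
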